3.4 Intervention

The intervention for subjects randomized to the Eradicate Trial is *Eloctate* ITI 100 IU/kg IV every other day plus Emicizumab 1.5 mg/kg SQ weekly (after 4-week induction at 3 mg/kg/week) vs. Eloctate ITI at 100 IU/kg every other day alone. *Eloctate* is an FDA-approved drug that was shown in clinical trials to be safe and effective in prevention and treatment of bleeds, with improved half-life and safety comparable to standard rFVIII with no differences in inhibitor frequency, thrombosis or allergic reaction. Emicizumab is an FDA-approved bispecific monoclonal antibody FVIII mimic that was shown in clinical trials to be safe and effective in the prevention of bleeds and is increasingly being used because of its simpler subcutaneous once weekly dosing. Parents, caretakers, or patients will review and provide written consent, after which subjects will be randomized by computer-generated randomization codes by the INHIBIT DCC Data Management System. Data will be stored in a secure database, housed in a locked room, which will track each drug prescription and infusion, including the initial dose within 24 hours of enrollment, and continued every other day for 48 weeks. *Eloctate* will be reconstituted by two-way needle to allow transfer of the diluent into the lyophilized powder and given by slow intravenous infusion over 5-10 minutes by heplock in an arm or hand vein; and Emicizumab will be given by subcutaneous injection by tuberculin syringe, which will allow transfer of the drug from the vial for injection over 1-2 minutes, in the abdomen, by HTC study nurse, visiting nurse, or trained parent/caretaker. Elocate and Emicizumab are covered by insurance, and prescriptions will be provided to patients/ parents/ caretaker by HTC MDs. Both drugs are FDA approved, Eloctate, exempt under IND 15996, and/or Emicizumab prophylaxis, as used in this trial, and thus, "exempt" from IND requirement.

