hypothesize that tolerance induction with Eloctate ITI plus Emicizumab is superior to Eloctate ITI alone in eradicating inhibitors in children and adults with severe hemophilia A and inhibitors. **Objective:** The **Primary Objective** is to determine if Eloctate ITI plus Emicizumab is different from Eloctate ITI alone in eradicating inhibitors in severe hemophilia A patients with high-responding inhibitors who are ITI-refractory or ITI-naïve, or those arising during the Inhibitor Prevention Trial. The Secondary Objectives are to evaluate the safety and mechanism of Eloctate ITI plus Emicizumab vs. Eloctate ITI alone in eradicating inhibitor eradication. The Primary Endpoint is the probability of becoming inhibitor-free by 48 weeks, where the **Endpoints:** eradication of inhibitor formation is defined as anti-FVIII < 0.6 B.U. by chromogenic Nijmegen Bethesda assay (CBA). The Secondary Endpoints include a) safety by number and frequency of bleeding episodes (i.e. hematoma, joint, CNS bleed) and frequency and time to port infections; and b) mechanism of inhibitor suppression (eradication) by FVIII-specific T cell ELISPOT assay, B cell, Ig, and RNA assays and cytokine assays to determine the role of T regs in controlling immune response to FVIII; and by FVIII genotype; HLA type; and chromogenic FVIII trough levels; and by micriobiome stool sample, each compared with anti-FVIII. **Study Population:** Study subjects will be male adults and children age > 4 months of age with severe hemophilia A, defined as factor VIII < 0.01 IU/ml and a current or past high-responding inhibitor (anti-FVIII >5.0 B.U.), either ITI-refractory, ITI-naïve, or developing on the linked Inhibitor Prevention Trial. A total of 90 eligible severe hemophilia A patients with inhibitors will be enrolled in this 6-year trial. Site Enrolling Subjects: There are up to 41 participating sites: Hemophilia Treatment Center (HTCs). **Description of Study** There are two study interventions: Eloctate ITI plus Emicizumab vs. Eloctate ITI alone. Intervention: Recombinant factor VIII Fc (Eloctate[®]) is an FDA-approved clotting factor approved for treatment and/or prevention of bleeds in hemophilia A. It is an intravenous agent supplied as single-use vials containing approximately 250, 500, 750 IU per vial. The vials are reconstituted with 5-10 ml vial of sterile water for injection, USP, which is transferred by two-way needle into the lyophilized powder for reconstitution, and the reconstituted vial infused over 5-10 minutes, at 65 IU/kg once weekly for 48 weeks. Emicizumab (Hemlibra®) is an FDA-approved agent for the prevention of bleeding in hemophilia A. It is a subcutaneous agent supplied in vial sizes of approximately 30 mg per ml, 60 mg per 0.4 ml, and 105 mg per 0.7 ml. A tuberculin syringe allows transfer of the drug from the vial for subcutaneous injection over 1-2 minutes, at 1.5 mg/kg weekly (following a 4-week induction with 3.0 mg/kg/week) for up to 48 weeks. **Trial Arms** Arm A Eloctate 100 IU/kg IV qod plus Emicizumab 1.5 mg/kg SQ weekly (after 3.0 mg/kg/wk x 4 wk) for 48 weeks Eloctate 100 IU/kg IV god alone for 48 weeks Arm B

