1.0 Objective and Specific Aims

The purpose of the Inhibitor Eradication Trial is to eradicate inhibitor formation in children and adults with severe hemophilia A. This 48-week phase III open-label, randomized, controlled trial, comparing *Eloctate* immune tolerance induction (ITI) plus the bispecific monoclonal antibody FVIII mimic, Emicizumab, vs. Eloctate ITI alone, to eradicate inhibitor formation in children and adults with severe hemophilia A, including those developing inhibitors in the Prevention Trial or those ITI-refractory or ITI-naïve never-tolerized inhibitors at the same HTCs. In this trial, time to inhibitor eradication with Eloctate ITI plus Emicizumab vs. Eloctate ITI will be assessed in the eradication of inhibitor formation in children and adults with severe hemophilia A and current or past high-responding inhibitors, defined as anti-FVIII > 5.0 B.U. The research in this trial is considered greater than minimal risk as it involves combining agents to eradicate inhibitors and obtaining special inhibitor studies. The primary endpoint will be the probability of inhibitor eradication by 48 weeks, defined as anti-FVIII < 0.6 B.U. by chromogenic Nijmegen Bethesda assay (CBA), repeated immediately and confirmed within 4 weeks. Secondary endpoints will include a) safety, measured by frequency of bleeds (hematomas, joint, CNS bleeds) and b) mechanism of inhibitor eradication, measured by FVIII-specific T cell ELISPOT assay, performed on peripheral blood mononuclear cells (PBMCs) at baseline and at 4, 12, 24, 36, and 48 weeks. The B cell, Ig, and RNA assays and cytokine assays will be performed on an aliquot of PBMCs to determine the role of T regs in eradication of immune response to FVIII. Studies will be performed on T cell populations depleted of regulatory T cells (T reg) (CD4+CD25+FoxP3+) to determine the role of T regs in controlling immune response to FVIII. Hemophilia genotype and HLA assays will be determined at baseline on the buffy coat of plasma. A microbiome (stool sample) will be obtained at baseline. The trial will assess inhibitor eradication after each subject completes the 48-week trial. The Inhibitor Eradication Trial is designed to test whether Eloctate ITI plus Emicizumab is superior to Eloctate ITI alone in inhibitor eradication by 48 weeks. At the interim, once 75% of the subjects are randomized, the Bayesian posterior probability that either arm, Eloctate ITI plus Emicizumab or Eloctate ITI alone, is more likely to be inhibitor-free must be at least 99.5% to stop the trial. Assuming that the trial does not stop at the interim to declare superiority at the end of the trial, the Bayesian posterior probability that either arm, *Eloctate ITI plus Emicizumab* or *Eloctate ITI* alone, is more likely to be inhibitor-free must be at least 97.9%. This maintains the type 1 error at 5% with at least 80% power for superiority if we assume that the true condition is that Eloctate ITI plus Emicizumab is 15% superior to Eloctate ITI alone (95% vs 80% inhibitor-free).

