3.0 Research Design and Methods

3.1 Drug/Device Information

Eloctate (rFVIIIFc) and *Emicizumab* (hemlibra) are FDA-approved for the prevention and/or treatment of bleeds in hemophilia A, and are safe and effective in adults, adolescents, and children. For this trial, subjects will use their own supply of study drug to which they are randomized. Clinical trials of *Eloctate* and *Emicizumab* in adults and children with severe hemophilia A have demonstrated safety and efficacy when used to prevent bleeds or promote hemostasis. In this trial, subjects will use *Eloctate* ITI (immune tolerance induction) with or without *Emicizumab* to eradicate inhibitors: this approach is supported by preliminary data from anecdotal small, non-randomized studies. Subjects will maintain a home inventory of the study drug(s) to which they are randomized. *Eloctate* in vial sizes of approximately 250, 500, and 750 is available for children, and 1000, 1500, 2000, 3000 IU for adults: a two-way needle will allow transfer of the diluent into the lyophilized powder for reconstitution and slow infusion over 5-10 minutes. *Emicizumab* in vial sizes of approximately 30 mg per ml, 60 mg per 0.4 ml, 105 mg per 0.7 ml, and 150 mg per ml is available for children and adults: a tuberculin syringe will allow transfer of the drug from the vial for subcutaneous injection over 1-2 minutes. Study drug(s) will be available by physician prescription which can be filled at the HTC pharmacy or at another pharmacy of the patient's or parent/caretaker's choice.

Once a subject is consented and identified as eligible for the trial, a unique subject number will be assigned to each subject by the Data Coordinating Center (DCC), Graduate School of Public Health (GSPH), University of Pittsburgh, Pittsburgh, PA. Study drug dosing will be given by the hemophilia center nurse, clinic or hospital infusion center, or, if on home treatment, by patient or parent/ care provider, or visiting nurse, in the usual manner: this is either by intravenous infusion (*Eloctate*) over 5-10 minutes through a winged infusion needle (butterfly) heplock placed in the forearm, or, if required, a central line; or by subcutaneous injection (*Emiczumab*) over 1-2 minutes with a tuberculin syringe in the abdomen or thigh. This study site will maintain accurate records, demonstrating dates, times, and doses administered, and patients or parent/caretakers will maintain a diary to record this information.

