The primary endpoint will be eradication of an inhibitor, defined as anti-FVIII < 0.6 B.U. by chromogenic Nijmegen Bethesda assay (CBA). A local lab anti-FVIII < 0.6 B.U. will be repeated on this sample or, if insufficient, a repeat sample within 7 days, and a second sample obtained within 4 weeks for confirmation. A central lab anti-FVIII < 0.6 B.U. will be repeated within 4 weeks for confirmation. A central lab anti-FVIII < 0.6 B.U. will be repeated within 4 weeks for confirmation. A central lab anti-FVIII < 0.6 B.U. will be repeated within 4 weeks for confirmation. All subjects whose inhibitor is eradicated will remain on study follow-up to week 48. Additional tests will be done, per standard of care, including peak and trough to advise when ITI can be stopped and regular prophylaxis can begin. Subjects whose inhibitor is eradicated, i.e. anti-FVIII < 0.6 B will receive *Eloctate* with/without *Emicizumab*, per physician discretion, to treat or prevent bleeds: if bleeding occurs that is unresponsive to *Eloctate* with/without *Emicizumab*, rFVIIa will be used. FEIBA will not be allowed on this trial for safety reasons.

It is anticipated that 2-4 subjects will be enrolled locally, contributing to the overall study enrollment of 90 subjects at one of up to 41+ participating HTCs. The duration of the study is approximately 48 weeks per subject, with an expectation the study will last up to 7 or more years, subject to enrollment and completion of all procedures. For this study, all study visits will occur at the HTC.

SCREENING VISIT, RANDOMIZATION, AND INITIATION OF ASSIGNED TREATMENT Study Visit 1, Screening/ Baseline Visit, Wk 0

This visit will take place prior to administration of *Eloctate* with/without *Emicizumab* in order to confirm eligibility requirements. Randomization and initiation of treatment may occur at this visit or within 4 weeks of the visit. The following tests or assessment will be performed at the Screening/ Baseline Visit.

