- The patient or parent/caretaker will obtain *Eloctate* with/without *Emicizumab* by physician prescription through a clotting factor pharmacy of their choice. *Eloctate* will be administered by venipuncture, using a winged infusion needle (butterfly needle), heplock, or, if required, by central line per physician discretion, over 5-10 minutes. *Emicizumab* will be administered by subcutaneous injection, using a small tuberculin needle over 1-2 minutes. It is anticipated in children and some adults that all study drug doses will be administered in the Hemophilia Center, or, for those living a distance away from the HTC, at a nearby infusion center, emergency room, by patient or parent/ caretaker if trained, or by a visiting nurse.
- All doses of study drug(s), including day, date, time, and dose will be recorded in subject diaries. All bleeds, including day, date, site, and resolution will be recorded by the patient or parent/caretaker. All diaries will be returned to the HTC nurse coordinator at the monthly visits.
- Subjects will begin *Eloctate* with/without *Emicizumab*, with the first dose as early as the day of consent and randomization, should the subject already have received a prescription and supply of study drug as part of standard care; otherwise, study drug(s) may be started as soon as the prescription is received.
- The weekly dose of study drug, 100 IU/kg *Eloctate ITI* with/without 1.5 mg/kg *Emicizumab* (following the 3.0 mg/kg weekly x 4 weeks induction), will be begun following enrollment and screening. The HTC nurse will discuss study visit scheduling with the patient or parent /caretaker. The Screening/ Baseline visit, which may include randomization ant treatment initiation, will last approximately 1 hour.

FOLLOW-UP VISITS:

Study Visit 2: Week 4 (Month 1) Follow-up Visit

- Subject diaries will be reviewed for accuracy and completeness. Data will be extracted for frequency, type, and site of bleeds, including site, and for factor usage by day, date, time, and dose.
- Study drug(s) use will be reviewed and more *Eloctate* with/without *Emicizumab* ordered as needed.
- Concomitant medications will be recorded.
- Assessment for adverse events will be completed.
- Vital signs [blood pressure (BP), pulse (P), respiratory rate (RR), and oral temperature (°C)] will be taken, and weight (kg) will be obtained.

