The **Primary Endpoint** is the probability of becoming inhibitor-free by 48 weeks, where the eradication of inhibitor formation is defined as anti-FVIII < 0.6 B.U. by chromogenic Nijmegen Bethesda assay (CBA). We *hypothesize* that tolerance induction with *Eloctate ITI* plus *Emicizumab* is superior to *Eloctate ITI* alone in eradicating inhibitors in children and adults with severe hemophilia A and inhibitors. While both drugs may shorten ITI and even be synergistic, there is equipoise.

Analysis of the Primary Endpoint: We propose to take advantage of prior historical information on inhibitor formation to improve power on the Prevention Trial, and efficient use of inhibitors developing on the Prevention Trial (PRO19040140) to enroll in the Eradication Trial. For the **Eradication Trial**, we propose a Bayesian design and analysis plan to test if *Eloctate* ITI plus *Emicizumab* is superior to *Eloctate ITI* alone. Given the lack of data on either arm, we used two non-informative priors and 1:1 randomization allocation. Non-informative Bayesian priors were used for both arms as there are no published data regarding the time to inhibitor eradication with *Emicizumab* or Eloctate. The time to inhibitor eradication will be compared between the two assigned treatment arms by piecewise exponential survival models to determine the probability of being inhibitor-free at 48 weeks. Monte-Carol Markov-Chains (MCMC) were utilized to determine the posterior probability of the outcome when determining the operating characteristics. At the interim, once 75% of the subjects are randomized, the Bayesian posterior probability that either *Eloctate ITI plus Emicizumab* or *Eloctate ITI alone* is more likely to be inhibitor-free must be at least 99.5% to stop the trial. Assuming the trial did not stop at the interim, then to declare significance at the end of the trial, the Bayesian posterior probability that either arm, *Eloctate ITI*

plus Emicizumab or *Eloctate ITI alone* is more likely to be inhibitor-free at must be 97.9%. This maintains type 1 error at 5%, two-sided, with at least 80% power for superiority if we assume the true condition is that *Eloctate ITI plus Emicizumab* has an inhibitor-free rate of 95% and Eloctate ITI has an inhibitor-free rate of 80%.

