5.0 Costs and Payments

5.1 Research Study Costs

No costs will be incurred by the subjects or their parents/care providers for their participation in this study for research procedures. sIRB preparation costs will be covered, along with research procedures, including screening visits, blood draws for local and central laboratory assays, blood processing, shipping, and HTC charges and services related this study protocol. *Eloctate or Emicizumab* in this study will be the patient's own study drug. The budget is not designed to cover the cost of factor. Should a central line be suggested by the subject's physician, there will be no payment or compensation as this is considered standard clinical care. Research blood draw kits will be provided by the University of Pittsburgh coordinating center for use at local HTC's. Any other expenses for this study not listed above, will be paid by the local HTC.

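### Access to the assigned drugs is not confirmed before randomisation, and failure to obtain Emicizumab departs from assignment only in Arm A

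*Combined protocol and SAP*

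**What the plan says.** Both drugs come from outside the trial. Section 3.1: "For this trial, subjects will use their own supply of study drug to which they are randomized". Section 5.1: "The budget is not designed to cover the cost of factor". Section 3.4 treats coverage as settled: "Elocate and Emicizumab are covered by insurance, and prescriptions will be provided to patients/ parents/ caretaker by HTC MDs".

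Neither list of criteria (3.5 and 4.3) asks for coverage or drug in hand, and the Visit 1 steps in 3.2 contain no access check. Eligibility is determined, the subject is randomised, and drug is then obtained by prescription. A subject who already holds drug may start the same day; "otherwise, study drug(s) may be started as soon as the prescription is received".

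The statements on timing do not agree:

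- Section 3.2, Visit 1: "Randomization and initiation of treatment may occur at this visit or within 4 weeks of the visit".
- Section 3.4 describes a first dose within 24 hours of enrollment.
- Section 4.4 places enrollment just before drug administration, while the first Visit 1 bullet in 3.2 ties it to signing consent.

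On analysis, the Treatment Period text in 3.2 keeps a subject who receives another clotting protein in the primary intention-to-treat analysis, and 3.6 compares the arms as assigned. Section 4.4 says that subjects withdrawn after enrollment but before receiving study drug are replaced. Sections 3.3, 3.4 and 3.6 provide for recording drug use and presenting adherence. No non-receipt rate, and no allowance for one, is given.

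**The concern.** Whether a subject can obtain the assigned regimen may first become known after the allocation is known, and the two regimens do not ask the same of the payer. Both arms need Eloctate; only Arm A also needs Emicizumab. Two different problems follow.

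1. **Dilution.** An Arm A subject who gets Eloctate but never Emicizumab receives the Arm B regimen and is counted in Arm A. The expected difference shrinks and power falls.
2. **Exclusion after randomisation.** A subject who gets no drug and withdraws is replaced. Section 4.4 does not say whether that subject stays in the analysis. If replaced means dropped, as it usually does, the analysed set depends on events after allocation that can differ by arm. The direction of that bias cannot be predicted.

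With 90 subjects in a rare disease, there is little room for either.

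**Working it through.** **Inputs from the documents**

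- Sample size: "A total of 90 eligible severe hemophilia A patients with inhibitors will be enrolled in this 6-year trial" (protocol summary). Allocation is 1:1 (3.6), so 45 per arm.
- Effect: "95% vs 80% inhibitor-free" (1.0).
- Stated performance: "This maintains type 1 error at 5%, two-sided, with at least 80% power for superiority" (3.6).
- Decision rule: posterior probability of 99.5% at an interim when 75% are randomised, and 97.9% at the end (1.0, 3.6).

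**Assumed**

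- A share d of Arm A, from 5% to 20%, never receives Emicizumab, responds at the Arm B rate of 80%, and stays in Arm A.

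**Step 1. The plan's own power**

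The primary model is time to eradication, so use Schoenfeld's formula with constant hazards:

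- HR = ln(1 − pA) / ln(1 − pB) = ln(0.05) / ln(0.20) = 1.861, and ln HR = 0.621
- Expected events D = 45 × (0.95 + 0.80) = 78.75
- Power = Φ(√D × ln HR / 2 − 1.96) = Φ(8.874 × 0.621 / 2 − 1.96) = Φ(0.797) = 78.7%

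This is within 2 points of the stated 80%, on the low side.

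**Step 2. Dilution**

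The Arm A rate becomes 0.95 − d × 0.15. The same formulas give:

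| d | Arm A rate | Difference | HR | Power, N = 90 | Total N for 80% power |
|---|---|---|---|---|---|
| 0 | 95.0% | 15.0 points | 1.861 | 78.7% | 94 |
| 5% | 94.25% | 14.25 points | 1.775 | 71.9% | 111 |
| 10% | 93.5% | 13.5 points | 1.698 | 64.8% | 130 |
| 20% | 92.0% | 12.0 points | 1.569 | 50.9% | 181 |

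**Step 3. Check against the Bayesian rule**

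The rule was simulated with constant hazards, vague gamma priors, uniform accrual over 6 years and the interim at the 68th subject (0.75 × 90 = 67.5). Type I error was 4.7%. Power was 76.6% with full access, 66.4% at d = 10% and 54.4% at d = 20%. The pattern agrees with step 2.

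The starting level depends on the model. With four hazard pieces per arm, simulated power was 61.1% with full access, 48.8% at d = 10% and 38.0% at d = 20%. The plan gives neither the number of pieces nor the prior parameters.

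**Step 4. Excluding subjects without access, compared with randomising them**

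Suppose candidates without access are not randomised and not replaced. At 10%, N = 81, D = 81 × 0.875 = 70.9, and power = Φ(8.419 × 0.621 / 2 − 1.96) = 74.4%, against 64.8% if they are randomised and the effect is diluted. At 20%, N = 72, D = 63, and power = 69.3%, against 50.9%.

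**The case against.** **The arms may not differ much in practice.** A reader might infer that non-receipt falls mainly on Arm A. The documents do not support that. They give no refusal rate for either drug. They describe Emicizumab as approved for preventing bleeds and increasingly used, and the approved uses they list for Eloctate are treatment and prevention of bleeds, not tolerance induction. Refusal of Eloctate would affect both arms. What stands is narrower: only the added Emicizumab step is specific to Arm A.

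**Supply may be in hand at randomisation.** Sections 3.4 and 4.4 imply an almost immediate start. But 3.2 provides expressly for subjects still waiting for a prescription. These statements need reconciling; they do not amount to an access check.

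**The intention-to-treat sentence concerns another clotting protein, not missing drug.** True, but 3.6 compares assigned arms, so the Eloctate-only subject would still count in Arm A.

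**Adherence is already recorded and will be presented.** This stands. A reader might infer that a null result could not be interpreted; the adherence data would in fact help. They would not restore lost power.

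**The range is invented, and dilution can come from Arm B too.** Both points stand. The 5% to 20% is an assumption, and it models subjects who never receive Emicizumab, not those who receive it late. Current Emicizumab users may enter if they stop first (3.2, 4.3). If 5%, 10% or 20% of Arm B resumed it and responded at 95%, Schoenfeld power would be 75.8%, 72.5% or 65.2%. An access check would not prevent that.

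**The check costs recruits in proportion to the problem.** To randomise 90, one would need 90 / 0.90 = 100 candidates if 10% lack access, or 90 / 0.80 = 112.5, so 113, if 20% do. This is a real cost, but step 4 shows that even without replacing those candidates power is higher than when they are randomised and diluted.

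**Conclusion.** The point holds as a gap in the design with an inexpensive remedy, at modest severity. No step before randomisation confirms access to the regimens, non-receipt of Emicizumab departs from assignment only in Arm A, and the replacement rule in 4.4 conflicts with intention-to-treat if it reaches randomised subjects. An Arm A subject who gets Eloctate alone dilutes the effect; one who gets nothing and is replaced introduces a bias of unknown direction.

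The size cannot be estimated from the documents. The fall from about 79% to 72%, 65% or 51% illustrates 5%, 10% or 20% non-receipt under constant hazards, with non-receivers responding at 80%. It should not be read as the power this trial will have.

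**What to change.** 1. In 3.2 (Visit 1) and 4.4, add a step before the Data Coordinating Center releases the allocation: the site records that the subject can obtain both Eloctate and Emicizumab, by payer approval or supply in hand. Complete it within the 4-week interval that 3.2 already allows, and randomise only then. Asking about both drugs for every subject keeps the check independent of arm.
2. In 4.4, limit replacement to subjects who leave before randomisation. State in 3.6 that every randomised subject is analysed in the assigned arm, whether or not drug was received.
3. Use the drug-use and adherence data already planned in 3.3, 3.4 and 3.6 to tabulate non-receipt of each assigned drug by arm.
4. Reconcile the statements in 3.2, 3.4 and 4.4 on when enrollment occurs and when treatment starts relative to randomisation.

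The cost is protocol wording, an eCRF item, payer paperwork for both drugs, and a short wait for some subjects. Candidates without access to either drug are not randomised. Their number equals the unknown refusal rate, and the population narrows accordingly.
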